10.1 Multiplicity

Gate-keeping methods will be used to control the overall Type 1 error rate for the key secondary endpoints. After the result from the primary efficacy analysis in the ITT population shows statistical significance, the key secondary endpoint 1 will be tested next. The key secondary endpoint 2 will be tested only if the test results for both primary endpoint and the key secondary endpoint 1 are significant. The key secondary endpoint 3 will be tested only if the test results for primary endpoint and the key secondary endpoints 1 and 2 are all significant. The testing procedure above will be implemented strictly in order to control the overall Type 1 error rate of 0.05 due to multiplicity.

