4.2.2. Secondary Efficacy Endpoints

4.2.2.1. Key Secondary Efficacy Endpoints

The analyses of secondary efficacy endpoints will be performed on the ITT population. The key secondary endpoints will be measured from Dose 1 Day 1 of the DBTP, and will be statistically tested in a sequential order at two-sided $\alpha = 0.05$ level (details related to multiplicity adjustment can be found in Section 10.1). The key secondary efficacy endpoints include:

- Mean change from baseline in NTDT-PRO Tiredness and Weakness (T/W) domain score over a continuous 12-week interval from Week 13 to Week 24.
- Mean hemoglobin change from baseline over a continuous 12-week interval from Week 13 to 24 in the absence of transfusion.
- Proportion of subjects who have an increase from baseline ≥ 1.0 g/dL in mean of hemoglobin values over a continuous 12-week interval from Week 37 to Week 48 in the absence of transfusions.

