4.4. Sample Size Determination

Based on the assumption of targeted primary endpoint response rates of at least 50% in the luspatercept group and 10% for the placebo group, and 2:1 randomization, a total sample size of

150 (100 in the luspatercept group, 50 in the placebo group) will have at least 99% power to detect the difference between the 2 groups with a 2-sided alpha of 0.05 and assumed 10% dropout rate.

For NTDT-PRO T/W domain scores, assume the mean change from baseline scores at Week 24 are 1.2 and 0.5 for luspatercept and placebo group, respectively, with a common standard deviation of 1.2, the statistical power will be 91%.

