 - c. Average of all Hb measurements in Weeks 14-25 (Day 93 to Day 176) if Weeks 14-25 has ≥ 3 Hb measurements
 - d. When the number of Hb measurements is less than 3 among Weeks 13-24, Weeks 12-23, and Weeks 14-25, then choose the largest number of Hb measurements in the following order as Hb at Week 13-24:
 - 1) Hb in Week 13-24
 - 2) Hb in Week 12-23

- 3) Hb in Week 14-25
 - e. Otherwise, missing
 - Weeks 37 - 48 interval: Same rule as Week 13-24 interval
- The calculation of weekly NTDT-PRO scores is detailed in Section 18.3.1. The 12-week interval score is obtained by averaging all the weekly scores (at least one non-missing) in these 12 weeks. If all the weekly scores in these 12 weeks are missing, the 12-week interval score is then declared missing.

This SAP addresses efficacy and safety endpoints during the double-blinded treatment period (including the initial 48-week treatment period for all subjects and the long-term treatment period for early enrolled subjects). The database will be locked upon all subjects completed 48 weeks of the double-blind treatment period or discontinued before reaching 48 weeks. All the data collected up to data cutoff date will be used for summary. Data selection rules will be applied in each summary panel as needed, please refer to individual part for details.

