10 EFFICACY ANALYSIS

All efficacy evaluations will be conducted using the ITT population with the exception of FACIT-F Fatigue Subscale (SF) and SF-36 analyses that will be conducted on the HRQoL evaluable population. NTDT-PRO T/W and SoB scores will be analyzed by both ITT and HRQoL populations. The primary and key secondary endpoints will also be analyzed based on the Per Protocol population as a sensitivity analysis.

Some continuous variables like hemoglobin and weekly NTDT-PRO T/W and SoB domains will be derived as the sum of results over 12 weeks divided by the number of assessments. The mean over 12 weeks will be used to derive mean change from baseline for each subject.

For the early treatment-discontinued subjects, i.e. subjects who did not complete 24 weeks or 48 weeks of double-blinded treatment period, the transfusion and assessment records (including Hb and QoL) will still be collected up to 48 weeks post Dose 1 Day 1 or 9 weeks post last dose, whichever is the later date. All the assessments before the efficacy cutoff date will be used to evaluate primary and secondary endpoints. For these endpoints, if at the time of data summary, a subject has died or has not reached the end of the 12-week interval, this subject will be included in the analysis. For other efficacy endpoints, the collected records will be used (by visits or at specified time point) as needed, depending on the purpose of the summary. Please refer to the individual endpoint section for details.

The efficacy cutoff date is defined as the minimum date among death date, study discontinuation date, last dose date + 20, and data cutoff date. For the primary and responder-related secondary endpoints, if at the time of data summary, a subject's efficacy cutoff date is before the end of the 12-week interval or a subject has any invalid hemoglobin records (i.e., within 21 days following a transfusion) during the specified 12-week interval, this subject will be included in the analysis and his/her responder status will be classified in accordance with the definition of erythroid response in Section 10.2. For other efficacy endpoints, if a subject's efficacy cutoff date is before the end of the 12-week interval, the subject will be included in the analyses.

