10.3 Analyses of Key Secondary Efficacy Endpoints

The analyses of key secondary efficacy endpoints will be performed on the ITT population. The key secondary endpoints will be tested in the order as mentioned from Section 10.1 and listed below:

- 1 Mean change from baseline in NTD-PRO Tiredness and Weakness (T/W) domain score over a continuous 12-week interval from Week 13 to Week 24.
- 2 Mean hemoglobin change from baseline over 12-week interval from Week 13 to 24 during the treatment period in the absence of transfusions.
- 3 Proportion of subjects who have an increase from baseline ≥ 1.0 g/dL in mean of hemoglobin values over a continuous 12-week interval from Week 37 to Week 48 in the absence of transfusions.

To control the overall Type 1 error rate for secondary endpoints, the testing procedure will be implemented strictly in order: the test for key secondary endpoint 1 will only be conducted when there is evidence showing that erythroid response is achieved in the luspatercept group from Week 13 to Week 24 (primary endpoint). The key secondary endpoint 2 will be tested only if the test results for both primary endpoint and the key secondary endpoint 1 are significant. The key secondary endpoint 3 will be tested only if the test results for primary endpoint and the key secondary endpoints 1 and 2 are all significant.

10.3.1 NTD-PRO (T/W Domain) Mean Change Between Weeks 13 to 24

The change from baseline on mean of NTD-PRO (T/W domain) over a 12-week interval between Weeks 13 to 24 will be analyzed using analysis of covariance (ANCOVA) method with treatment group in the model and randomization stratification factor(s) as covariates. Treatment effect will be evaluated as a contrast of luspatercept versus placebo. Least squares (LS) means with

corresponding standard errors (SE) for each treatment group, along with LS mean of treatment difference with corresponding 95% CI and p-value will be presented.

The subgroup analyses including baseline NTDT-PRO T/W (≥ 3 and <3) will be performed as described in Section 10.5.

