10.4 Analyses of Other Secondary Efficacy Endpoints

The analyses of other secondary efficacy endpoints will be performed on the ITT population except for the FACIT-F and SF-36 endpoints listed in this section. The analyses of NTDT-PRO, FACIT-F, and SF-36 endpoints will be conducted based on the Health Related QoL evaluable population (Section 5.2.4).

10.4.1 FACIT-F Fatigue Subscale (FS): Mean Change from Baseline between Weeks 13 to 24 and Weeks 37 to 48

Mean FACIT-F FS score change from baseline over a 12-week interval between Weeks 13 to 24 (nominal Dose 5 to Dose 9) will be analyzed using ANCOVA method with treatment group, randomization stratification factor(s) in the model and baseline FACIT-F FS score as covariate. The baseline of FACIT-F FS is the score from the last visit prior to or on Dose 1 Day 1.

Mean change from baseline for Weeks 37 to 48 (nominal Dose 13 to Dose 17) will be analyzed similarly.

The subgroup analyses for Weeks 13-24 will be performed as described in Section 10.5.

10.4.2 NTDT-PRO SoB Score: Mean Change from Baseline between Weeks 13 to 24 and Weeks 37 to 48

Mean NTDT-PRO SoB score change from baseline over a 12-week interval between Weeks 13 to 24 will be analyzed using ANCOVA method with treatment group, randomization stratification factor(s) in the model and baseline NTDT-PRO SoB score as covariate. Similar analysis will be performed for Weeks 37 to 48.

10.4.3 Hemoglobin Mean Change Between Weeks 37 to 48

Mean Hemoglobin change from baseline over 12-week interval between Weeks 37 to 48 during the treatment period will be analyzed using ANCOVA method with treatment group and randomization stratification factor(s) in the model as covariates.

Baseline hemoglobin (Hb) is the average of 2 or more Hb measurements at least 1 week apart within 4 weeks prior to Dose 1 Day 1. The Hb values within 21 days following a transfusion may be influenced by the transfusion and will be excluded from this analysis. For discontinued subjects who do not complete 24 weeks of the DBTP, Hb data will continue to be collected. For a subject, if the Hb average over Weeks 37-48 interval cannot be calculated due to missing data, the closest Hb 12-week average will be used.

10.4.4 NTDI-PRO (T/W Domain) Mean Change Between Weeks 37 to 48

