18.3 QoL Algorithm

18.3.1 NTDT-PRO (Non-Transfusion-Dependent Thalassemia Patient-Reported Outcome)

The NTDT-PRO is a disease-specific QoL tool used to assess the severity of symptoms associated with NTDT β -thalassemia. It is administered as a daily eDiary with recall of thalassemia-related symptoms during the past 24 hours.

Baseline and post-baseline score calculations are performed based on weekly item scores. Baseline scores are calculated over 7 days prior to Dose 1 Day 1. The NTDT-PRO scores are recorded daily from Dose 1 Day 1 through Week 24. After Week 24, the NTDT-PRO scores are recorded by visit. The Week 1 weekly scores are calculated from Day 1 to Day 7. The Week 2 weekly scores are calculated from Day 8 to Day 14, similarly through the Week 24 weekly scores. After Week 24, the weekly scores will be derived over 7 days based on the closest visit day.

Step 1: Scoring the Items

All items have score ranges from 0–10, with higher scores indicating more severe symptoms. If entries are missing for ≥ 4 days in any week, the average weekly item score is declared as missing. Otherwise the mean of the non-missing item values is taken.

If subjects do not have any valid NTDT-PRO scores at baseline, Week 13-24 or Week 37-48 due to the minimum 4-day non-missing weekly score requirement, the 4-day non-missing rule will be relaxed to at least 2 days to avoid missing data. The justification of this relaxed rule is supported by the simulation results showing that no significant difference is found between 4-day and 2-day non-missing weekly scores (*Psychometric assessment of the NTDT-PRO using data from the phase 2 luspatercept study, 2020*).

Step 2: Calculating Scores for the T/W Domain

The average of non-missing weekly item scores from the first 4 items (i.e., TiredNA, TiredPA, WeakNA, WeakPA) will be calculated if at least 1 non-missing weekly item score for tiredness [i.e. TiredNA, TiredPA] and at least 1 non-missing weekly item score for weakness [i.e. WeakNA, WeakPA]; otherwise, the weekly T/W score will be set to missing. Thus, the range of weekly T/W score is 0–10.

Step 3: Calculating Scores for the SoB Domain

The average of non-missing weekly item scores from the last 2 items (i.e., SobNA and SobPA) will be calculated if $\geq 50\%$ of the items (≥ 1 items) are not missing; otherwise, the weekly SoB score will be set to missing. Thus, the range of weekly SoB score is 0–10.

NTDT-PRO© (version 2) Instrument

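### Should hemoglobin mean change at Weeks 13-24 be tested before the NTDT-PRO tiredness/weakness score in the fixed sequence?

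*SAP*

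**What the plan says.** SAP 10.1, SAP 10.3 and Protocol 9.6.2 give the same strict order:

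1. primary: Hb response (increase of at least 1.0 g/dL), Weeks 13-24
2. key secondary 1: change in NTDT-PRO T/W, Weeks 13-24
3. key secondary 2, worded in SAP 10.3 as "Mean hemoglobin change from baseline over 12-week interval from Week 13 to 24 during the treatment period in the absence of transfusions"
4. key secondary 3: Hb response, Weeks 37-48

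SAP 4.2.2.1 adds that the key secondaries "will be statistically tested in a sequential order at two-sided" 0.05. The gate in question is in SAP 10.1: "key secondary endpoint 2 will be tested only if the test results for both primary endpoint and the key secondary endpoint 1 are significant".

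On power, SAP 4.4 (and Protocol 9.3) states at least 99% for the primary at 50% vs 10% response with 100 and 50 subjects and 10% drop-out. For T/W it takes mean changes of 1.2 and 0.5 and continues: "with a common standard deviation of 1.2, the statistical power will be 91" per cent. Neither document gives an effect, SD or power for Hb mean change, and the visible text gives no reason for the order.

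**The concern.** In a fixed sequence every test runs at the full 0.05. A later position therefore costs an endpoint only the chance that an earlier test fails. This favors putting the surest endpoint first. Here the order looks reversed: T/W has a planned failure rate of about 9%, while Hb mean change uses the same Hb values as the primary and should rarely fail once the primary has passed. A T/W miss stops formal testing before Hb mean change is reached. At stake is a claim the sponsor chose to place under error control, and exchanging the two steps would appear to protect it almost free of charge.

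**Working it through.** **Inputs from SAP 4.4.** Allocation 100:50; two-sided alpha 0.05; response 50% vs 10%; T/W difference 1.2 - 0.5 = 0.7; SD 1.2; 10% drop-out, stated in the primary-endpoint sentence only.

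**Assumed, because the documents do not say.** Hb change is normal with equal SD in both arms; the T/W-Hb correlation is 0 to 0.5.

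**1. The stated T/W power.** Noncentrality = 0.7 / (1.2 × √(1/100 + 1/50)) = 0.7 / 0.2078 = 3.37.

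- Normal approximation: Φ(3.37 - 1.96) = 92.0%
- Noncentral t: 91.7%

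The stated 91% is reproduced.

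**2. T/W power with drop-out.** At 90:45 the noncentrality is 0.7 / (1.2 × √(1/90 + 1/45)) = 3.20, and power is 89.2% (normal) or 88.7% (t). This requires every drop-out to have no T/W value at all. SAP 5.1 makes that hard: "The 12-week interval score is obtained by averaging all the weekly scores (at least one non-missing) in these 12 weeks". The efficacy cutoff in SAP 10 is the "minimum date among death date, study discontinuation date, last dose date + 20, and data cutoff date". Dose n nominally falls on Day 1 + 21(n - 1), so Dose 4 is Day 64 and its cutoff is Day 84. Under SAP 18.3.1 ("The Week 1 weekly scores are calculated from Day 1 to Day 7"), Week 13 starts on Day 85. On the nominal schedule a drop-out therefore lacks a Weeks 13-24 score only if dosing stopped by Dose 4. The 90:45 case is pessimistic about drop-out, although missing diaries could remove other subjects.

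**3. Implied power for Hb mean change.** A cut at 1.0 g/dL giving 50% and 10% responders implies a difference of z(0.50) - z(0.10) = 1.28 SD. Noncentrality is 1.28 / √(1/100 + 1/50) = 7.4, or 7.0 at 90:45. Power exceeds 99.9% in both cases.

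**4. Hb claim lost only through a T/W miss.** With Hb power near 1, this is about 1 minus T/W power:

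| T/W power | Share of trials |
|---|---|
| 91% as stated | 9.0% |
| 91.7% (t, 100:50) | 8.3% |
| 88.7% (t, 90:45) | 11.3% |

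Joint simulation, 40,000 trials per setting, gave 8.2-8.6% at 100:50 and 11.4% at 90:45.

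**5. Cost to T/W of the reverse order.** This is the chance that T/W passes and Hb mean change fails.

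| Setting | Cost (points) |
|---|---|
| Normal, equal SD | 0.0 |
| Responder/non-responder mixtures, 100:50 | 0.5-1.2 |
| Same mixtures, 90:45 | 0.8-2.1 |
| Normal, luspatercept SD 2 × placebo SD | 0.1-0.5 |
| Ratio 2.5 | 2-4 |
| Ratio 3 (extreme) | about 8-13 |

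**6. Effect of the planned model.** These figures use unadjusted tests, but SAP 10.3.1 specifies ANCOVA with the stratification factors, one of which is baseline T/W category. If those factors explained 5, 10 or 20% of T/W variance (an assumption), the noncentrality divides by √(1 - R²) and T/W power at 100:50 becomes 93.0, 94.1 or 96.3%. The loss in step 4 then falls to about 7, 6 or 4%.

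**7. What the arithmetic leaves out.** The net gain in claims from reversing is P(Hb passes, T/W fails) - P(T/W passes, Hb fails) = Hb power - T/W power. It is positive whenever the Hb effect exceeds the T/W effect of 0.7/1.2 = 0.58 SD, which corresponds to about 24% vs 10% responders. This comparison treats the two claims as equally valuable. The plan does not:

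- T/W is the only key secondary with a stated effect, SD and power (SAP 4.4).
- Baseline T/W is one of two stratification factors (SAP 4.3).
- NTDT-PRO is the first-listed secondary objective (SAP 3.2).
- A dedicated responder threshold was derived for it (SAP 10.4.16).

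Hb mean change, by contrast, shares the variable, window, baseline and transfusion exclusion of the primary (SAP 10.2 and 10.3.2). In every trial counted in step 4 the primary has already succeeded, and SAP 10 has the Hb difference, interval and p-value reported regardless. Hb response at Weeks 37-48 needs all three earlier tests to pass in either order, so it gains nothing.

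**The case for a change.** The best case for reversing is that it takes little from T/W. T/W would keep its full alpha and, under 50% vs 10% response, lose about 2 points at most unless the arms' Hb SDs differ by a factor of about 2.5 or more. The 8-9% also assumes that the full T/W difference of 0.7 is real. If it were 0.5 (an assumption), T/W power would be about 67% and roughly 33% of trials would forfeit the formal Hb mean change claim. The documents' visible text does not explain the order, so an intended priority is inferred.

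The numbers stand, and so does the general principle that surer endpoints placed early cost less. They do not turn a valid order into a wrong one. The reverse order would put an endpoint with no stated effect or power ahead of the one the plan powered, to secure a formal label on a near-duplicate of the primary.

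The timing also counts against it. Reversing needs a protocol amendment after enrollment was complete (SAP 16) and after Weeks 13-24 NTDT-PRO data had been used before database lock to set the responder threshold (SAP 10.4.16). Moving T/W down at that stage would invite the suspicion that the data had prompted it, even though the sponsor has no access to unblinded data (Protocol 9.10.3).

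**Conclusion.** The concern does not hold. The sequence is fully specified, identical across the documents, and controls the family-wise error at 0.05. Its price is real but limited: about 8-9% of trials would lose the formal Hb mean change claim through a T/W miss alone, about 11% if all drop-outs lack T/W scores, and perhaps 4-7% if the stratification factors explain 5-20% of T/W variance. These figures assume 50% vs 10% response, a T/W difference of 0.7 with SD 1.2, and Hb mean change power near 100%, which is inferred because the plan gives none. What is lost is a label on the continuous form of an endpoint already won, with the estimate still reported. Placing the powered patient-reported endpoint first is a defensible priority on which experienced statisticians may differ. The plan needs no change on this point.

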10.2 Analysis of Primary Efficacy Endpoint

The primary efficacy endpoint of this study is erythroid response, defined as an increase from baseline ≥ 1.0 g/dL in mean of hemoglobin values over a continuous 12-week interval from Weeks 13 to 24 in the absence of transfusions. The response rate is defined as the number of responders divided by the number of subjects in the ITT population within each treatment group.

Baseline hemoglobin (Hb) is the average of 2 or more Hb measurements at least 1 week apart within 4 weeks prior to Dose 1 Day 1. The Hb values within 21 days following a transfusion may be influenced by the transfusion and will be excluded from this analysis. For discontinued subjects who do not complete 24 weeks of the DBTP, Hb data will continue to be collected. For a subject, if the Hb average over Weeks 13-24 interval cannot be calculated due to missing data, the closest Hb 12-week average will be used as mentioned in Section 5.1. If the 12-week average is still missing, the imputation method will be performed as described in Section 10.6.1 and the responder status will be classified in accordance with the definition of erythroid response in Section 10.2.

The number and percentage of subjects in the ITT population who achieve the response will be calculated for luspatercept and placebo. The primary efficacy analysis for treatment comparison (luspatercept versus placebo) will be conducted by the Cochran Mantel-Haenszel (CMH) test with the treatment and randomization stratification factor(s) in the model. The odds ratio (OR) (luspatercept versus placebo) with corresponding 95% confidence interval (CI) and p-value will be calculated with treatment group, randomization stratification factor(s) in the model to compare the luspatercept and placebo groups at 2-sided 0.05 level. In addition, the difference in response rate

between luspatercept and placebo with corresponding 95% CI will be calculated by exact unconditional test.

A forest plot showing the ORs, 95% CI and p-value for the overall result and the results in each subgroup will be constructed. Listing of individual Hb data will be provided.

The subgroup analyses described in Section 10.5, including mean baseline Hb (≥ 8.5 g/dL and < 8.5 g/dL) for the primary endpoint will also be performed by summarizing the response rate difference and OR with corresponding 95% CI.

A sensitivity analysis will be conducted by classifying subjects with less than 3 Hb measurements from Week 13 (-7 days) to Week 24 (+7 days) as non-evaluable and excluded in the analysis. Additional sensitivity analysis will be conducted by classifying those non-evaluable subjects as non-responders. The same sensitivity analysis will be followed for Hb secondary endpoints over Weeks 37 to 48. Additional sensitivity analyses for the missing assessments are stated in Section 10.6.1.

10.3 Analyses of Key Secondary Efficacy Endpoints

The analyses of key secondary efficacy endpoints will be performed on the ITT population. The key secondary endpoints will be tested in the order as mentioned from Section 10.1 and listed below:

- 1 Mean change from baseline in NTD-PRO Tiredness and Weakness (T/W) domain score over a continuous 12-week interval from Week 13 to Week 24.
- 2 Mean hemoglobin change from baseline over 12-week interval from Week 13 to 24 during the treatment period in the absence of transfusions.
- 3 Proportion of subjects who have an increase from baseline ≥ 1.0 g/dL in mean of hemoglobin values over a continuous 12-week interval from Week 37 to Week 48 in the absence of transfusions.

To control the overall Type 1 error rate for secondary endpoints, the testing procedure will be implemented strictly in order: the test for key secondary endpoint 1 will only be conducted when there is evidence showing that erythroid response is achieved in the luspatercept group from Week 13 to Week 24 (primary endpoint). The key secondary endpoint 2 will be tested only if the test results for both primary endpoint and the key secondary endpoint 1 are significant. The key secondary endpoint 3 will be tested only if the test results for primary endpoint and the key secondary endpoints 1 and 2 are all significant.

10.3.1 NTD-PRO (T/W Domain) Mean Change Between Weeks 13 to 24

The change from baseline on mean of NTD-PRO (T/W domain) over a 12-week interval between Weeks 13 to 24 will be analyzed using analysis of covariance (ANCOVA) method with treatment group in the model and randomization stratification factor(s) as covariates. Treatment effect will be evaluated as a contrast of luspatercept versus placebo. Least squares (LS) means with

corresponding standard errors (SE) for each treatment group, along with LS mean of treatment difference with corresponding 95% CI and p-value will be presented.

The subgroup analyses including baseline NTDT-PRO T/W (≥ 3 and <3) will be performed as described in Section 10.5.

The treatment-by-stratification-factor(s) interaction will be added to the ANCOVA model as a sensitivity analysis and results from this model will be compared to the primary fixed effects model (without the interaction effect). If the interaction is significant at a 2-sided 0.1-alpha level, the nature of this interaction will be inspected as to whether it is quantitative (that is, the treatment effect is consistent in direction but not in size of effect) or qualitative (the treatment is beneficial in some values of the stratification factor(s)). If the interaction effect is found to be quantitative, results from the primary fixed effect model will be presented. If the interaction effect is found to be qualitative, further inspection will be used to identify in what values of the stratification factor(s) the treatment is more beneficial.

10.3.2 Hemoglobin Mean Change Between Weeks 13 to 24

Mean Hb change from baseline over a 12-week interval between Weeks 13 to 24 will be analyzed using ANCOVA method with treatment group in the model and randomization stratification factor(s) as covariates. Treatment effect will be evaluated as a contrast of luspatercept versus placebo. Least squares (LS) means with corresponding standard errors (SE) for each treatment group, along with LS mean of treatment difference with corresponding 95% CI and p-value will be presented.

Baseline hemoglobin (Hb) is the average of 2 or more Hb measurements at least 1 week apart within 4 weeks prior to Dose 1 Day 1. The Hb values within 21 days following a transfusion may be influenced by the transfusion and will be excluded from this analysis. For discontinued subjects who do not complete 24 weeks of the DBTP, Hb data will continue to be collected. For a subject, if the Hb average over Weeks 13-24 interval cannot be calculated due to missing data, the closest Hb 12-week average will be used as described in Section 5.1. If the value is still missing, the imputation method will be performed as described in Section 10.6.1.

A waterfall plot will be provided for the hemoglobin change from baseline by treatment group. Individual subject's hemoglobin change from baseline will be displayed in a single bar. The displayed hemoglobin change is each subject's largest decrease in hemoglobin.

The subgroup analyses including mean baseline Hb (≥ 8.5 g/dL and <8.5 g/dL) will be performed, as described in Section 10.5.

10.3.3 Hemoglobin Response Between Weeks 37 to 48

Hemoglobin responder, defined as an increase from baseline ≥ 1.0 g/dL in mean of hemoglobin values over a continuous 12-week interval from Weeks 37 to 48 in the absence of transfusions will be analyzed.

Baseline hemoglobin (Hb) is the average of 2 or more Hb measurements at least 1 week apart within 4 weeks prior to Dose 1 Day 1. The Hb values within 21 days following a transfusion may be influenced by the transfusion and will be excluded from this analysis. For discontinued subjects who do not complete 24 weeks of the DBTP, Hb data will continue to be collected. For a subject,

if the Hb average over Weeks 37-48 interval cannot be calculated due to missing data, the closest Hb 12-week average will be used.

The number and percentage of subjects in the ITT population who achieve the response will be calculated for luspatercept and placebo. The odds ratio (OR) (luspatercept versus placebo) with corresponding 95% CI and p-value will be provided and the CMH chi-square test will be conducted with treatment group and randomization stratification factor(s) in the model to compare the luspatercept and placebo groups at 2-sided 0.05 level. The difference in proportions (Luspatercept minus placebo) with corresponding 95% CI will be calculated by exact unconditional test.

The subgroup analyses including mean baseline Hb (≥ 8.5 g/dL and < 8.5 g/dL) will be performed, as described in Section 10.5.

